9 PROGRAMMING SPECIFICATIONS

The rules for programming derivations and dataset specifications are provided in separate documents.

10 STATISTICAL SOFTWARE

All statistical analyses will be performed by Eisai Inc., using SAS Version 9.4. Tessella will use a validated algorithm to run the Bayesian NDLM.

11 MOCK TABLES, LISTINGS AND GRAPHS (TLGS)

The study TLG shells will be provided in a separate document, which will show the content and format of all tables, listings, and graphs in detail.

13 APPENDICES

13.1 Sponsor's Grading for Determining Markedly Abnormal Laboratory Results

The following table of Sponsor's Grading for Laboratory Values is copied from the protocol, [Appendix 1](#).

Sponsor's Grading for Laboratory Values				
	Grade 1	Grade 2	Grade 3	Grade 4
BLOOD/BONE MARROW				
Hemoglobin	< LLN – 10.0 g/dL < LLN – 100 g/L < LLN – 6.2 mmol/L	< 10.0 – 8.0 g/dL < 100 – 80 g/L < 6.2 – 4.9 mmol/L	< 8.0 g/dL < 80 g/L < 4.9 mmol/L; transfusion indicated	life-threatening consequences; urgent intervention indicated
Leukocytes (total WBC)	< LLN – 3.0 x 10 ⁹ /L < LLN – 3000/mm ³	< 3.0 – 2.0 x 10 ⁹ /L < 3000 – 2000/mm ³	< 2.0 – 1.0 x 10 ⁹ /L < 2000 – 1000/mm ³	< 1.0 x 10 ⁹ /L < 1000/mm ³
Lymphocytes	< LLN – 800/mm ³ < LLN – 0.8 x 10 ⁹ /L	< 800 – 500/mm ³ < 0.8 – 0.5 x 10 ⁹ /L	< 500 – 200/mm ³ < 0.5 – 0.2 x 10 ⁹ /L	< 200/mm ³ < 0.2 x 10 ⁹ /L
Neutrophils	< LLN – 1.5 x 10 ⁹ /L < LLN – 1500/mm ³	< 1.5 – 1.0 x 10 ⁹ /L < 1500 – 1000/mm ³	< 1.0 – 0.5 x 10 ⁹ /L < 1000 – 500/mm ³	< 0.5 x 10 ⁹ /L < 500/mm ³
Platelets	< LLN – 75.0 x 10 ⁹ /L < LLN – 75,000/mm ³	< 75.0 – 50.0 x 10 ⁹ /L < 75,000 – 50,000/mm ³	< 50.0 – 25.0 x 10 ⁹ /L < 50,000 – 25,000/mm ³	< 25.0 x 10 ⁹ /L < 25,000/mm ³
METABOLIC/LABORATORY				
Albumin, serum- low (hypoalbuminemia)	< LLN – 3 g/dL < LLN – 30 g/L	< 3 – 2 g/dL < 30 – 20 g/L	< 2 g/dL < 20 g/L	life-threatening consequences; urgent intervention indicated
Alkaline phosphatase	> ULN – 3.0 x ULN	> 3.0 – 5.0 x ULN	> 5.0 – 20.0 x ULN	> 20.0 x ULN
ALT	> ULN – 3.0 x ULN	> 3.0 – 5.0 x ULN	> 5.0 – 20.0 x ULN	> 20.0 x ULN
AST	> ULN – 3.0 x ULN	> 3.0 – 5.0 x ULN	> 5.0 – 20.0 x ULN	> 20.0 x ULN
Bicarbonate, serum-low	< LLN – 16 mmol/L	< 16 – 11 mmol/L	< 11 – 8 mmol/L	< 8 mmol/L
Bilirubin (hyperbilirubinemia)	> ULN – 1.5 x ULN	> 1.5 – 3.0 x ULN	> 3.0 – 10.0 x ULN	> 10.0 x ULN
Calcium, serum-low (hypocalcemia)	< LLN – 8.0 mg/dL < LLN – 2.0 mmol/L	< 8.0 – 7.0 mg/dL < 2.0 – 1.75 mmol/L	< 7.0 – 6.0 mg/dL < 1.75 – 1.5 mmol/L	< 6.0 mg/dL < 1.5 mmol/L
Calcium, serum-high (hypercalcemia)	> ULN – 11.5 mg/dL > ULN – 2.9 mmol/L	> 11.5 – 12.5 mg/dL > 2.9 – 3.1 mmol/L	> 12.5 – 13.5 mg/dL > 3.1 – 3.4 mmol/L	> 13.5 mg/dL > 3.4 mmol/L
Cholesterol, serum-high (hypercholesterolemia)	> ULN – 300 mg/dL > ULN – 7.75 mmol/L	> 300 – 400 mg/dL > 7.75 – 10.34 mmol/L	> 400 – 500 mg/dL > 10.34 – 12.92 mmol/L	> 500 mg/dL > 12.92 mmol/L
Creatinine	> ULN – 1.5 x ULN	> 1.5 – 3.0 x ULN	> 3.0 – 6.0 x ULN	> 6.0 x ULN
GGT (γ-Glutamyl transpeptidase)	> ULN – 3.0 x ULN	> 3.0 – 5.0 x ULN	> 5.0 – 20.0 x ULN	> 20.0 x ULN
Glucose, serum-high (hyperglycemia)	Fasting glucose value: > ULN – 160 mg/dL > ULN – 8.9 mmol/L	Fasting glucose value: > 160 – 250 mg/dL > 8.9 – 13.9 mmol/L	> 250 – 500 mg/dL; > 13.9 – 27.8 mmol/L; hospitalization indicated	> 500 mg/dL; > 27.8 mmol/L; life-threatening consequences
Glucose, serum-low (hypoglycemia)	< LLN – 55 mg/dL < LLN – 3.0 mmol/L	< 55 – 40 mg/dL < 3.0 – 2.2 mmol/L	< 40 – 30 mg/dL < 2.2 – 1.7 mmol/L	< 30 mg/dL < 1.7 mmol/L life-threatening consequences; seizures
Phosphate, serum-low (hypophosphatemia)	< LLN – 2.5 mg/dL < LLN – 0.8 mmol/L	< 2.5 – 2.0 mg/dL < 0.8 – 0.6 mmol/L	< 2.0 – 1.0 mg/dL < 0.6 – 0.3 mmol/L	< 1.0 mg/dL < 0.3 mmol/L

Sponsor's Grading for Laboratory Values				
	Grade 1	Grade 2	Grade 3	Grade 4
				life-threatening consequences
Potassium, serum-high (hyperkalemia)	> ULN – 5.5 mmol/L	> 5.5 – 6.0 mmol/L	> 6.0 – 7.0 mmol/L hospitalization indicated	> 7.0 mmol/L life-threatening consequences
Potassium, serum-low (hypokalemia)	< LLN – 3.0 mmol/L	< LLN – 3.0 mmol/L; symptomatic; intervention indicated	< 3.0 – 2.5 mmol/L hospitalization indicated	< 2.5 mmol/L life-threatening consequences
Sodium, serum-high (hypernatremia)	> ULN – 150 mmol/L	> 150 – 155 mmol/L	> 155 – 160 mmol/L hospitalization indicated	> 160 mmol/L life-threatening consequences
Sodium, serum-low (hyponatremia)	< LLN – 130 mmol/L	N/A	< 130 – 120 mmol/L	< 120 mmol/L life-threatening consequences
Triglyceride, serum-high (hypertriglyceridemia)	150 – 300 mg/dL 1.71 – 3.42 mmol/L	> 300 – 500 mg/dL > 3.42 – 5.7 mmol/L	> 500 – 1000 mg/dL > 5.7 – 11.4 mmol/L	> 1000 mg/dL > 11.4 mmol/L life-threatening consequences
Uric acid, serum-high (hyperuricemia)	> ULN – 10 mg/dL ≤ 0.59 mmol/L without physiologic consequences	N/A	> ULN – 10 mg/dL ≤ 0.59 mmol/L with physiologic consequences	> 10 mg/dL > 0.59 mmol/L life-threatening consequences

ALT = alanine aminotransferase (serum glutamic pyruvic transaminase), AST = aspartate aminotransferase (serum glutamic oxaloacetic transaminase), GGT = γ -glutamyl transpeptidase, N/A = not applicable, LLN = lower limit of normal, ULN = upper limit of normal, WBC = white blood cell.

Based on Common Terminology Criteria for Adverse events (CTCAE) Version 4.0. Published: May 28, 2009 (v4.03: June 14, 2010).

13.2 Study Simulation Plan

Appendix 13.2 presents the simulation plan and details the Normal Dynamic Linear Model, simulations, design, and operating characteristics.

1.0 INTRODUCTION

This is a phase II dose-finding study of BAN2401 for the treatment of Alzheimer's disease. The minimum sample size will be 196 patients and the maximum sample size will be 800 patients. We use response adaptive randomization to allocate patients between placebo control and 5 active doses with the goal of characterizing the dose response curve. The study will be monitored for early success and early futility. There are two schedules of administration, bi-weekly and once monthly. The primary endpoint is the change in a composite clinical score from baseline to 52 weeks. A difference from control of at least 0.03 would be considered a clinically significant difference (CSD).

2.0 STATISTICAL MODELING

2.1 Primary Endpoint Modeling

The primary endpoint is the change from baseline to 52 weeks in a composite clinical score. We label the observations of the change from baseline in composite clinical score for subject i , at the 6, 12, 26, 39, and 52 week visits as $Y_{i,6}$, $Y_{i,12}$, $Y_{i,26}$, $Y_{i,39}$, and $Y_{i,52}$, respectively. We model the 52-week primary outcomes as normally distributed,

$$[Y_{i,52}] \sim N(\theta_d, \sigma^2),$$

where d_i is the treatment arm for subject i . The treatment arms are: $d=0$ (control), $d=1$ (3 mg/kg bi-weekly), $d=2$ (5 mg/kg bi-weekly), $d=3$ (10 mg/kg bi-weekly), $d=4$ (5 mg/kg monthly), and $d=5$ (10 mg/kg monthly). □

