Subjects will be from 2 clinical subgroups, collectively designated as EAD for the purposes of this protocol: (a) MCI due to AD – intermediate likelihood and (b) mild Alzheimer's disease dementia. At study entry, subjects will be stratified according to clinical subgroup, *APOE* status (*APOE4* positive and negative), and the presence or absence of ongoing AD treatment with AChEIs or memantine or both. Randomization into the 2 clinical subgroups (see [Inclusion Criteria, Section 9.3.1 of the protocol](#)) is to remain reasonably balanced whereby at least 60% of the total number of subjects will have MCI due to AD – intermediate likelihood clinical subgroup and at least 30% will have mild Alzheimer's disease dementia. The subjects will be randomized into 1 of 6 treatment groups ([Table 1](#)) as explained in [Section 9.4.4](#) and [Section 9.4.5 of the protocol](#). *APOE4* status (positive or negative) must be confirmed for all subjects prior to randomization. After Protocol Amendment 05 based on the request from the Voluntary Harmonisation Procedure (VHP) committee, subjects who are confirmed *APOE4* positive (*APOE4* hetero- or homozygous) will not be randomized to the 10 mg/kg, biweekly dose. Randomization in the Core Study will initially be fixed to each of these dose groups (4:2:2:2:2:2 ratio, placebo to each of the 5 active treatment arms). All study personnel and subjects will be blinded with respect to the dose regimens. After 196 subjects have been randomized into the study, an interim analysis (IA) will be conducted and RAR will guide subsequent randomization into dose groups. Interim analyses and RAR will be repeated after 250 subjects have been randomized and again after each additional 50 subjects until all 800 subjects are randomized, and will then be conducted at 3-month intervals until all subjects complete 12 months of

treatment. A Bayesian analysis will be conducted at 12 months of treatment to assess for early success, and at 18 months of treatment, regardless of whether early success is achieved at 12 months.

Table 1 BAN2401 Dose Regimens

Study Arm	BAN2401 Dose (mg/kg)	Infusion frequency
1	Placebo	Biweekly ^a
2	2.5	Biweekly ^a
3	5.0	Biweekly ^a
4	10.0 ^b	Biweekly ^a
5	5.0	4-week intervals ^c
6	10.0	4-week intervals ^c

a: Biweekly = 2-week intervals

b: Subjects who are confirmed *APOE4* positive (*APOE4* hetero-or homozygous) will not be randomized to the 10 mg/kg, biweekly dose.

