5.3.2 Adjustments for Covariates of Interest

The primary, secondary, and exploratory endpoints will include the stratification variables clinical subgroup (MCI due to AD, Mild Alzheimer's Disease Dementia), *APOE ε4 carrier status* (positive or negative) and the presence or absence of ongoing AD treatment (i.e., AChEIs and/or memantine). In addition, the following covariates of interest will be evaluated in the statistical models: Age (treated as continuous and as categorical age ≤ 65 , $65 < \text{age} < 80$, age ≥ 80 years), region and *APOE* alleles ($\epsilon 4/\epsilon 4$, $\epsilon 4/\text{other}$ and $\text{other}/\text{other}$)

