The key Secondary endpoints (ADCOMS, CDR-SB, and ADAS-Cog) will also be analyzed separately within subjects with MCI and mild AD dementia.

Change from baseline in the ADCOMS at 18 months will be analyzed, as a sensitivity analysis to the conventional analysis, using the same Bayesian methodology as that for analysis of change from baseline in the ADCOMS at 12 months, but using the full 18 months of efficacy data with the model projecting to 18 months of treatment. The Bayesian analysis of change from baseline in the ADCOMS at 18 months is positive if the analysis results in an ED₉₀ dose with at least an 80% probability of being better than the placebo by the CSD. The ED₉₀ dose will be identified based on change from baseline in the ADCOMS at the 18 month Bayesian analysis and will be used to compare ED₉₀ dose of BAN2401 and placebo in the above sensitivity analyses for all key secondary endpoint analyses.

Specifically, the following Bayesian analyses will be performed at 18 months:

- Fit the 2-dimensional NDLM Bayesian model defined in [Appendix 13.2](#) with 5 doses across 2 schedules of administration for the 18-month endpoint. This includes imputation of missing values from the longitudinal model.
- Compare placebo versus the combined 10mg dose group. This includes imputation of missing values from the longitudinal model.
- Fit a one-dimensional Bayesian model with 3 doses: 2.5mg dose group, combined 10mg dose group, and combined 5mg dose group. This will be a one-dimensional NDLM model with imputation of missing values from the longitudinal model.
- Fit the European Prevention of Alzheimer’s Dementia (EPAD) disease progression model for selected doses versus the placebo control.

In this study, subjects consented to PET sub-study have been using two different tracers for PET scan: Florbetapir and Flutemetamol. Only less than 10 subjects have used Flutemetamol and the rest have used Florbetapir. It is possible that different tracers may yield different results and data using different tracers may not be directly comparable, therefore only subjects using Florbetapir will be included in summary tables and other statistical analysis based on PET data. Subjects using Flutemetamol will only be listed and will not be included in summary tables or other statistical analysis based on PET data.

Other Secondary Endpoint Analyses

The same analysis described above for key secondary endpoints will be performed for other secondary endpoints.

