6.3 ADAPTIVE RANDOMIZATION

Subjects will receive 18 months of treatment. Randomization to placebo or one of five dose arms of BAN2401 will be fixed for the first 196 subjects randomized in the study (4:2:2:2:2:2; placebo to each of the five active arms). Randomization probabilities to each arm will be updated at each IA such that the randomization probability will be increased for the placebo arm and arms that represent the potential target dose (ED_{90}), and simultaneously decreased for other active arms. At the time of Amendment 05 of protocol, the sponsor has agreed to the request from the Voluntary Harmonisation Procedure (VHP) committee that subjects who are confirmed *APOE4* positive (*APOE4* hetero- or homozygous) not be randomized to the 10 mg/kg, biweekly dose. After each interim analysis after protocol Amendment 05, the randomization probability vector will be split between *APOE4+* and *APOE4-* strata to ensure no subjects are enrolled on the 10 mg/kg biweekly dose. The overall probabilities as suggested by RAR will still be preserved. Details on the derivation of the adaptive randomization probabilities, are found in the Simulation Plan, see [Appendix 13.2](#).

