2.2 Dose-Response Model Primary

We label the mean change from baseline to 52-weeks for dose group d as θ_d . We construct a dose-response model for the mean change from baseline for each treatment arm. The arms are modeled with a two-dimensional first-order normal dynamic linear model (NDLM). This model is a Gaussian random walk model. The structure is

$$\begin{aligned} [\theta_0] &\sim N(0, 0.5^2) \\ [\theta_1] &\sim N(0, 0.5^2) \end{aligned}$$

□

and the NDLM structure for the bi-monthly doses:

$$[\theta_2] \sim N(\theta_1, \tau^2)$$

□

$$[\theta_3] \sim N(\theta_2, \tau^2)$$

The monthly doses are “connected” to the dose-response model through the respective bi-monthly doses. The connection through the NDLM first order structure results in the following priors

$$[\theta_4] \sim N(\theta_2, \tau^2)$$

and

$$[\theta_5] \sim N\left(\frac{\theta_3 + \theta_4}{2}, \frac{\tau^2}{2}\right).$$

The drift parameter (variance component), τ^2 is modeled with the following prior distributions:

$$[\tau^2] \sim IG(0.25, 0.0025)$$

where $IG(a, b)$ is the inverse gamma distribution with shape parameter a and scale parameter b . This prior has the equivalent weight of 0.5 observations worth of weight that the value of τ is 0.1.

The prior distribution on the initial dose is selected to be a vague prior. An effect size of 0.03 is considered clinically significant and the standard error of the clinical scale is 0.15. Therefore these priors are quite weak and allow the data to shape the dose-response model. The prior for the “drift parameter” is selected to have minor weight that there will be similarity across the doses, and hence a minor amount of borrowing. With 5 doses the amount of borrowing is determined largely by the similarity in outcomes across doses.

The distribution of the variance of the primary endpoint, σ^2 , is modeled with the following prior:

$$[\sigma^2] \sim IG(2.5, 0.056).$$

The prior is equivalent to a prior weight of 5 observations worth of information that the value of σ is 0.15. The value of 0.15 is based on initial modeling by Eisai. This prior allows the historical data estimate of 0.15 to have some role in the early part of the trial. When 300 subjects have been enrolled this prior will have a very minor role (5/305 weight is less than 2%).

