2.3 Longitudinal Model

At each interim analysis there will be subjects who have complete or incomplete information. Some subjects will have complete information meaning they have a 52-week value observed, $Y_{i,52}$. These subjects may also have their earlier values observed, $Y_{i,6}$, $Y_{i,12}$, $Y_{i,26}$, and $Y_{i,39}$. There will be subjects with earlier observations, but no 52-week observation. There will be subjects with no observations.

We utilize the information from subjects with incomplete information to the extent that the earlier values are correlated to the final 52-week value. A Bayesian model is built to learn from the accruing information on the association between the early values and the final endpoint at 52 weeks. Different sets of parameters (instances) are used for each arm in the trial, but the models correlating early to late outcomes are the same.

A linear regression model is created for the correlation between the 6-, 12-, 26-, and 39-week values and the 52-week value (we suppress the subject index i and refer to the change from baseline at weeks 6, 12, 26, 39, and 52 as Y_6 , Y_{12} , Y_{26} , Y_{39} , and Z_{52}). A common model is used for each active dose and a separate model for the control. Each of the model instances is identical, with the following structure for early time period j :

$$\begin{aligned} [Z_{52} | Y_j] &\sim N(\alpha_j + \beta_j Y_j, \lambda_j^2) \\ [\alpha_j] &\sim N(0, 0.05^2) \\ [\beta_j] &\sim N(0.80, 0.25^2) \\ [\lambda_j^2] &\sim IG(2.5, 0.025). \end{aligned}$$

The prior distribution for the standard deviation about the linear regression, λ , has a prior mean estimate of 0.10 with a weight of 5 observations. The joint posterior distribution of α_j , β_j , and λ_j , for $j=6, 12, 26$, and 39 , are updated at each interim analysis (as described in [Section 4.0](#)) with the observed values of Y_{52} .

These prior distributions were selected from historical data provided by Eisai. The data were discounted to allow the new study to shape the posteriors, but these priors provide empirically based starting values.

At each interim analysis (as described in [Section 4.0](#)), this model is used, with Bayesian imputation within Markov chain Monte Carlo, to update the dose-response model at each interim analysis. The Markov chain Monte Carlo steps are as follows:

- 1). Simulate longitudinal model parameters from the updated joint posterior distribution

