3BM	0.01	0.252	0.602	0.381
5BM	0.008	0.161	0.585	0.348
10BM	0.009	0.168	0.593	0.355

Interim analyses are conducted again after 300 and 350 patients are enrolled and results are similar. The possibility for early success stopping begins at the 350 patient interim analysis. At the interim analysis when 400 patients have been enrolled, patients are beginning to complete the 52 weeks of follow-up for the primary endpoint (Table 7.3.A). Each of the BM doses have a positive observed effect at 39 weeks, but the 3BM dose also has a strong effect at 12 weeks and a patient with a large effect at 52 weeks. The 3BM dose is the most likely ED₉₀ (Table 7.3.B). The probability it is better than control by the CSD is 61%. Neither the early futility nor early success criteria are met. Accrual continues with the 3BM dose receiving a higher probability of randomization for the next 50 patients to be enrolled.

		No Data		6 Weeks		12 Weeks		26 Weeks		39 Weeks		52 Weeks	
	N	N	Obs	N	Obs	N	Obs	N	Obs	N	Obs	N	Obs
PBO	101	14	17	0.005	34	0.005	27	-0.012	9	-0.043	0	0	
5Q	63	12	11	-0.008	24	0.004	11	-0.001	4	-0.014	1	-0.001	
10Q	55	10	8	-0.005	18	0.016	12	-0.002	6	-0.029	1	0.208	
3BM	73	17	17	0.006	27	0.027	9	0.007	2	0.036	1	0.174	
5BM	53	11	5	0.006	18	0.014	14	0.011	3	0.095	2	-0.056	
10BM	55	7	11	0.006	17	0.007	13	0.012	6	0.086	1	0.085	

	Model Est	Pr(ED₉₀)	Pr(PBO)	Pr(CSD)
PBO	-0.005	-	-	-
5Q	0.001	0.07	0.57	0.284
10Q	0.024	0.277	0.744	0.502
3BM	0.037	0.414	0.838	0.606
5BM	0.003	0.042	0.568	0.281
10BM	0.026	0.196	0.761	0.507

Results are similar at the next interim analysis when 450 patients are enrolled. At the interim analysis with 500 patients enrolled, the 10BM dose now has the largest effect and the

randomization probabilities will shift such that the 10BM dose will receive a greater weight (Tables 7.4.A and 7.4.B).

	N	No Data		6 Weeks		12 Weeks		26 Weeks		39 Weeks		52 Weeks	
		N	Obs	N	Obs	N	Obs	N	Obs	N	Obs	N	Obs
PBO	129	17	16	0	38	0.012	26	-0.005	24	-0.001	8	0.016	
5Q	66	6	4	-0.015	24	0.005	18	0	9	0.009	5	-0.015	
10Q	69	8	10	-0.004	18	0.005	17	0.044	10	0.036	6	-0.021	
3BM	111	27	16	-0.006	40	0.018	17	0.052	8	0.026	3	0.099	
5BM	55	6	0	0	15	0.026	19	0.024	10	0.04	5	0.042	
10BM	70	9	10	0.008	15	0.02	20	0.039	10	0.007	6	0.119	

	Model Est	Pr(ED ₉₀)	Pr(PBO)	Pr(CSD)
PBO	0.017	-	-	-
5Q	-0.001	0.03	0.3	0.09
10Q	0.01	0.028	0.415	0.104
3BM	0.035	0.206	0.692	0.355
5BM	0.033	0.115	0.698	0.331
10BM	0.066	0.621	0.934	0.729

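### The Bayesian NDLM takes no account of APOE4 although allocation to 10 mg/kg biweekly depended on it, so its 12- and 18-month contrasts, and the 18-month ED90 drawn from them, are confounded if APOE4 is prognostic

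*SAP*

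**What the plan says.** **Bayesian model.** Appendix 13.2, section 2.1: "We model the 52-week primary outcomes as normally distributed", with mean theta_d for the arm and variance sigma^2. Section 2.2: "The arms are modeled with a two-dimensional first-order normal dynamic linear model (NDLM"; it links arm means to one another and to nothing else. Section 2.3 regresses the 52-week value on an earlier value alone: "A common model is used for each active dose and a separate model for the control". SAP Sections 5.4.1, 5.4.2.1 and 5.4.2.2 describe this model and add no covariate.

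**Covariate rule.** Section 5.3.2: "The primary, secondary, and exploratory endpoints will include the stratification variables clinical subgroup", followed by APOE4 carrier status and ongoing AD treatment. The rule is not limited to the conventional analyses.

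**Allocation.** Section 3.2 says that after Protocol Amendment 05 confirmed carriers "will not be randomized to the 10 mg/kg, biweekly dose. Randomization in the Core Study will initially be fixed to each of these dose groups". Section 6.3 splits the allocation vector by APOE4 and adds: "The overall probabilities as suggested by RAR will still be preserved". It refers to Appendix 13.2 for the derivation, but section 4.0 there gives a single unsplit vector.

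**18 months.** Section 5.4.4 reuses the two-dimensional NDLM, adds a one-dimensional version, and plans this: "Compare placebo versus the combined 10mg dose group. This includes imputation of missing values from the longitudinal model". No covariate is named for any of them. The ED90 from the 18-month Bayesian analysis then defines the ED90-versus-placebo comparison for all key secondary endpoints.

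**Conventional model.** The MMRM in Sections 5.4.1.2 and 5.4.4 does include APOE4 status and the other two stratification variables.

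**The concern.** The restriction itself is not at issue. What matters is that it made a stratification factor determine assignment to one arm part-way through randomization, and the model behind the primary analysis ignores that factor. If carriers and non-carriers progress at different rates, theta_3 minus theta_0 combines the drug effect with a difference in case mix. The NDLM can pass part of that on, because the prior for 10 mg/kg monthly is centred on the average of theta_3 and theta_4.

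Three things rest on this contrast: the probability that each dose is the ED90, the probability of beating placebo by the CSD, and the allocation at later looks. At 18 months the selected ED90 also fixes which arm enters an otherwise adjusted comparison. Finally, the operating characteristics in Appendix 13.2 describe a design without the split.

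**Working it through.** **1. Reproducing a figure from the plan.** Appendix 13.2, section 7.0, ends its example trial with model estimates of 0.012 (placebo, N = 185) and 0.067 (10 mg/kg biweekly, N = 160), and a probability of 0.923 of beating placebo by the CSD. With SD 0.15 (section 2.2), a normal approximation without covariates is

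Pr = Phi((0.055 - 0.03) / (0.15 × sqrt(1/n0 + 1/n3))).

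- All randomized (185/160): SE 0.0162, Pr = 0.939.
- Subjects with any data (178/151): SE 0.0166, Pr = 0.934.
- 52-week completers only (114/93): SE 0.0210, Pr = 0.884.

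The first two are within 2 points of 0.923. The SE implied by 0.923 is 0.025/1.4255 = 0.0175.

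**2. Carrier gap.** The SAP gives neither the carrier share c nor the exact count at the change. The request is dated July 2014, between the 300-subject (June 2014) and 350-subject (September 2014) interim reports, so I assume 325 before and 475 after. I also assume c = 50-70%, a share q = 20% to 10 mg/kg biweekly throughout, and displaced carriers spread evenly over the other arms.

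- Fraction randomized after the change: 475/800 = 0.594.
- Carriers in 10 mg/kg biweekly: 0.406c.
- Carriers in placebo: 0.406c + 0.594c/(1 - q).
- Gap: 0.594c/0.8 = 0.742c, which is 0.371 at c = 0.5 and 0.520 at c = 0.7.

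**3. Bias.** Bias = gap × assumed carrier/non-carrier difference in ADCOMS change. At 0.02 this is 0.0074 to 0.0104, or 25% to 35% of the 0.03 CSD. For scale, Section 5.4.2 equates the CSD with about 25% of placebo progression, which implies a placebo change near 0.12; 0.02 is about one sixth of that.

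**4. Effect on the example trial.** With SE 0.0175, shifting the estimate by 0.0074 moves 0.923 to 0.968 or 0.842, depending on direction. A shift of 0.0104 moves it to 0.978 or 0.798, about level with the 0.80 success bar.

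**5. Combined 10 mg group.** If the two 10 mg arms are equal in size, the gap halves to 19-26 points and the bias at 0.02 is 0.004-0.005. Pooling narrows the imbalance without removing it.

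**6. Simulation of the design.** A simulation of Appendix 13.2 (linear profile, 40% dropout, separate imputation parameters per arm) gave null success of 0.105 in 1,000 trials against the stated 0.125. This is an approximate match only. Section 2.3 describes both separate parameters per arm and one common active-dose model; the common version gave 0.01-0.035 in 200-trial runs.

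With c = 0.6, the split from the 350-subject look and no drug effect (600 trials per row):

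| Setting | 10 mg/kg biweekly chosen as ED90 | False success via that arm | Any false success |
|---|---|---|---|
| No APOE4 effect | 0.184 | 0.026 | 0.105 |
| Carriers worse by 0.03 | 0.325 | 0.052 | 0.128 |
| Carriers better by 0.03 | 0.103 | 0.015 | 0.100 |

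The first row is the 1,000-trial run. In the second row the carrier shares were 0.66 (placebo) and 0.30, so the bias is 0.03 × 0.36 = 0.011, close to the upper end of step 3.

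**7. Preserving the overall probabilities.** If only non-carriers can enter the arm, its overall share cannot exceed 1 - c. At the 500-subject look of the example trial, "randomization probabilities will shift such that the 10BM dose will receive a greater weight". The arm then grows from 70 to 160 while the total goes from 500 to 700: 90/200 = 45%, which is infeasible if carriers exceed 55%. In Table 9.2 the largest mean share after burn-in is (153.1 - 28)/(668.5 - 196) = 26% (scenario One Works).

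**The case against.** **The plan recognises the loss of carriers and responds to it.** It pools the 10 mg arms, adjusts the MMRM for APOE4, analyses APOE4 subgroups (Section 5.3.4), and labels the 18-month Bayesian ADCOMS analysis a sensitivity analysis to the conventional one. This stands. A reader might infer that the main 18-month inference is confounded by the missing adjustment; the documents do not support that. What remains exposed is the 12-month primary analysis, the 18-month Bayesian contrasts and the ED90 selection.

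**Section 5.3.2 can be read as met by the MMRM of the primary endpoint.** Fair: it never names the NDLM, so a flat contradiction is too strong. But it is not confined to conventional analyses either, and the primary analysis is Bayesian.

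**The size is assumed.** Correct. The documents give no carrier share, APOE4 effect or direction, so it cannot be said that the bias favours the drug. Other allocation histories move the gap: the simulation gave about 33-37 points at c = 0.6. Burn-in ratios for all of the first 325, followed by 20% to this arm and about 25% to placebo, would give 41-57. Overall null success of 0.128 against 0.105 is not clearly different (z about 1.4). The shift in which dose is selected is clearer.

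**Preserving the probabilities is not impossible.** Also correct. The 45% comes from one illustrative trial, and the 26% mean share lies below the 30-50% non-carrier share assumed here. The statement fails only if the arm's share exceeds the non-carrier share.

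**Conclusion.** The point holds in a limited form. The NDLM and its imputation regressions omit a factor that determined allocation to one arm after Amendment 05, so the 12- and 18-month NDLM contrasts, and to a lesser degree placebo versus combined 10 mg, are confounded if APOE4 is prognostic. Under the step 2 assumptions the carrier gap is about 37-52 points. A 0.02 difference in ADCOMS change then produces a bias of about 0.007-0.010, or 25-35% of the CSD, in an unknown direction. If APOE4 is neither prognostic nor effect-modifying, the bias is zero.

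Carriers could enter the arm before the change, so the imbalance is partial. The EPAD progression model planned for 18 months is not specified, and nothing is concluded about it.

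A reader might also infer that the 12-month primary analysis should be replaced. The 12-month interim reports are dated 05 Dec 2017 and SAP v4.0 is dated 05 Jun 2018, so only an added sensitivity analysis is open there.

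**What to change.** - **18-month Bayesian models.** Add APOE4 status, clinical subgroup and AD-treatment use, with weak normal priors, to the outcome model and to the regressions of the final score on earlier scores. Do this for the two-dimensional NDLM, the one-dimensional NDLM and placebo versus combined 10 mg. Take the 18-month ED90 from the adjusted model.
- **12 months.** Report the same adjusted model as a sensitivity analysis. State that additive adjustment assumes no treatment-by-APOE4 interaction, which matters because no carriers entered 10 mg/kg biweekly after the change.
- **Section 5.3.2.** Say which analyses include the stratification variables, in line with the above.
- **Appendix 13.2.** State that the operating characteristics do not include the APOE4 split, or re-simulate with it.
- **Section 6.3.** Qualify the statement on overall probabilities: it holds only while the share to 10 mg/kg biweekly does not exceed the non-carrier share.

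The cost is some model re-specification and simulation by the independent analysis group, plus reliance on the no-interaction assumption. No new subjects or data are needed.
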